10.4.2. Attribution Definitions

Assessment of Causality

The causal relationship to study vaccine is determined by the investigator. The following selection should be used to assess all AEs.

Related

There is a reasonable causal relationship between study vaccine administration and the AE.

Not Related

There is not a reasonable causal relationship between study vaccine administration and the AE.

The term “reasonable causal relationship” means there is evidence to support a causal relationship.

By definition, all solicited AEs at the injection site (local) will be considered related to the study vaccine administration.

10.4.3. Severity Criteria

All AEs and laboratory data will be coded for severity using a modified version of the FDA grading table, based on version of September 2007⁶³, included in [Appendix 9](#).

The AESI definition includes thrombocytopenia, defined as platelet count <150,000/ μ L as per the Brighton Collaboration (Section [8.3.7.1](#)).

For the purpose of severity grading, an AE of thrombocytopenia based on platelet counts >140,000/ μ L and <150,000 μ L should be considered Grade 1.

For AEs not identified in the grading table, the following guidelines will be applied:

Grade 1	Mild	Symptoms causing no or minimal interference with usual social and functional activities
Grade 2	Moderate	Symptoms causing greater than minimal interference with usual social and functional activities
Grade 3	Severe	Symptoms causing inability to perform usual social and functional activities and requires medical intervention
Grade 4	Potentially life-threatening	Symptoms causing inability to perform basic self-care functions OR medical or operative intervention indicated to prevent permanent impairment, persistent disability OR ER visit or hospitalization

For participants in the Safety Subset, the severity of solicited signs and symptoms will be graded in the e-Diary by the participant based on the severity assessment provided in the diary as well as assessed by the investigator using the toxicity grading scale in [Appendix 9](#). (Note: severity of the measured events will be derived from the diameter [for erythema and swelling] and the temperature measurements [for fever]). See also Section [8.3.2](#).

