7. DISCONTINUATION OF STUDY VACCINATION AND PARTICIPANT DISCONTINUATION/WITHDRAWAL

7.1. Discontinuation of Study Vaccination

Study vaccinations in the double-blind phase will be withheld for the reasons listed below. These participants must not receive any further doses of study vaccine but should remain on study for follow-up with assessments of safety, efficacy, and immunogenicity as indicated in the [Schedules of Activities](#). Additional unscheduled visits may be performed for safety/reactogenicity reasons, if needed. In case of questions, the investigator is encouraged to contact the sponsor.

- Any related AE, worsening of health status or intercurrent illnesses that, in the opinion of the investigator, requires discontinuation from study vaccine
- The participant becomes pregnant
- Unblinding on the participant level that, in the opinion of the sponsor, would compromise the integrity of the data
- Unblinding requested by a study participant in order to receive an authorized/licensed COVID-19 vaccine prior to general unblinding at the time of EUA in the US for the single-dose schedule of Ad26.COV2.S
- Anaphylactic reaction following vaccination, not attributable to causes other than vaccination
- SAE or other potentially life-threatening (Grade 4) event that is determined to be related to study vaccine
- Chronic or recurrent use of systemic corticosteroids and administration of antineoplastic and immunomodulating agents or radiotherapy
- Participant received any experimental medication (including experimental vaccines other than the study vaccine) or received a COVID-19 vaccine or treatment
- Withdrawal of consent to receive further study vaccination
- Participant has a molecularly confirmed SARS-CoV-2 infection based on samples collected within the study (see Section [8.1.2](#))
- Participant previously experienced TTS or HIT.

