10.4.1. Adverse Event Definitions and Classifications

Adverse Event

An AE is any untoward medical occurrence in a clinical study participant administered a pharmaceutical (investigational or non-investigational) product. An AE does not necessarily have a causal relationship with the vaccine. An AE can therefore be any unfavorable and unintended sign (including an abnormal finding), symptom, or disease temporally associated with the use of a medicinal (investigational or non-investigational) product, whether or not related to that medicinal (investigational or non-investigational) product. (Definition per ICH).

This includes any occurrence that is new in onset or aggravated in severity or frequency from the baseline condition, or abnormal results of diagnostic procedures, including laboratory test abnormalities.

For the Safety Subset, any respiratory tract infection will be reported as an AE if it occurs between the time of any vaccination through the following 28 days. Any respiratory tract infection recorded as an AE in the eCRF will be excluded from the AE analysis if the molecular test is subsequently found to be positive for SARS-CoV-2. Respiratory tract infections arising from SARS-CoV-2 infection will not be reported as (S)AEs in the Clinical Study Report but will be tabulated separately.

As of Protocol Amendment 7, COVID-19 will be reported as SAE, AE, or MAAE.

Note: For time period of sponsor's AE collection, see All Adverse Events under Section [8.3.1](#).

Serious Adverse Event

An SAE based on ICH and EU Guidelines on Pharmacovigilance for Medicinal Products for Human Use is any untoward medical occurrence that at any dose:

- Results in death
- Is life-threatening
(The participant was at risk of death at the time of the event. It does not refer to an event that hypothetically might have caused death if it were more severe)
- Requires inpatient hospitalization or prolongation of existing hospitalization
- Results in persistent or significant disability/incapacity
- Is a congenital anomaly/birth defect
- Is a suspected transmission of any infectious agent via a medicinal product
- Is Medically Important*

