Nausea [#]	Minimal symptoms; causes minimal or no interference with work, school, or self-care activities	Notable symptoms; Requires modification in activity or use of medications; Does NOT result in loss of work, school, or cancellation of social activities	Incapacitating symptoms; Requires bed rest and/or results in loss of work, school, or cancellation of social activities	Hospitalization; Inability to perform basic self-care functions
Diarrhea [#]	2 – 3 loose stools or <400 gms/24 hours	4 – 5 stools or 400 – 800 gms/24 hours	6 or more watery stools or >800 gms/24 hours or oral rehydration necessary	Hospitalization; Hypotensive shock OR IV fluid replacement indicated
Headache [#]	Minimal symptoms; causes minimal or no interference with work, school, or self-care activities	Notable symptoms; Requires modification in activity or use of medications; Does NOT result in loss of work, school, or cancellation of social activities	Incapacitating symptoms; Requires bed rest and/or results in loss of work, school, or cancellation of social activities; Use of narcotic pain reliever	Hospitalization; Inability to perform basic self-care functions
Fatigue [#]	Minimal symptoms; causes minimal or no interference with work, school, or self-care activities	Notable symptoms; Requires modification in activity or use of medications; Does NOT result in loss of work, school, or cancellation of social activities	Incapacitating symptoms; Requires bed rest and/or results in loss of work, school, or cancellation of social activities; Use of narcotic pain reliever	Hospitalization; Inability to perform basic self-care functions
Myalgia [#]	Minimal symptoms; causes minimal or no interference with work, school, or self-care activities	Notable symptoms; Requires modification in activity or use of medications; Does NOT result in loss of work, school, or cancellation of social activities	Incapacitating symptoms; Requires bed rest and/or results in loss of work, school, or cancellation of social activities; Use of narcotic pain reliever	Hospitalization; Inability to perform basic self-care functions

[#] Revised by the sponsor.

Systemic Illness	Mild (Grade 1)	Moderate (Grade 2)	Severe (Grade 3)	Potentially Life Threatening (Grade 4)
Illness or clinical adverse event (as defined according to applicable regulations)	No interference with activity	Some interference with activity not requiring medical intervention	Prevents daily activity and requires medical intervention	Hospitalization [#]

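### For clinical adverse events without their own row in Appendix 9, two Grade 4 definitions apply and disagree on emergency-room visits and self-care

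*Protocol*

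**What the plan says.** Section 10.4.3 makes Appendix 9 the default instrument: "All AEs and laboratory data will be coded for severity using a modified version of the FDA grading table". It then adds a second scale with a limited scope: "For AEs not identified in the grading table, the following guidelines will be applied". In that second scale Grade 4 covers inability to perform basic self-care, or "medical or operative intervention indicated to prevent permanent impairment, persistent disability OR ER visit or hospitalization".

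Most rows in Appendix 9 are for named findings: injection-site pain, erythema and swelling; fever and the other vital signs; vomiting, nausea, diarrhea, headache, fatigue and myalgia. The last row is generic: "Illness or clinical adverse event (as defined according to applicable regulations"). Its Grade 3 is "Prevents daily activity and requires medical intervention". Its Grade 4 is hospitalization only, marked as a sponsor revision.

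Section 7.1 uses the grade to withhold further study vaccine. One of its bullets reads "SAE or other potentially life-threatening (Grade 4) event that is determined to be related to study vaccine", and the same wording appears in both the double-blind and the open-label list.

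**The concern.** The fallback list in Section 10.4.3 and the generic row in Appendix 9 address the same group: clinical adverse events with no row of their own. They set Grade 4 at different points. A site that uses the list and a site that uses the generic row can both follow the protocol and still record different grades for the same event.

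This matters first for conduct, because Section 7.1 attaches a withholding rule to a related Grade 4 event. It matters second for analysis. The per-protocol efficacy and per-protocol immunogenicity populations both require two doses, so a second dose withheld in the double-blind phase removes the participant from both. Grading and withholding are done at the site under the protocol, and a statistical analysis plan cannot restore a dose that was not given.

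**Working it through.** No arithmetic applies. The check sets the two definitions side by side, works out which events fall under both, and follows the grade to the rules and outputs that use it.

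**Step 1: which events are in conflict.** The scope sentence in Section 10.4.3 excludes any event identified in the table. The named findings are therefore graded by Appendix 9 alone. Every solicited event in Section 8.3.2 (injection-site pain, erythema, swelling, fever, fatigue, headache, nausea, myalgia) has its own row, so none is in conflict. For the rest there are two readings:

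- If the generic row counts as identifying an event, the Section 10.4.3 list has almost nothing left to grade.
- If it does not, the generic row has no use.

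The protocol does not choose between them.

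**Step 2: where the two definitions differ.**

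| Feature of the event | Section 10.4.3 list | Appendix 9 generic row |
|---|---|---|
| Hospitalization | Grade 4 | Grade 4 |
| ER visit, not admitted | Grade 4 | Not a criterion; at most Grade 3 |
| Inability to perform basic self-care | Grade 4 | Not among the Grade 4 criteria |

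Two constructed records show the effect of the ER clause:

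- Dizziness treated in the ER, discharged the same day, usual activity prevented for that day: Grade 3 by the generic row, Grade 4 by the list.
- Mild rash checked in the ER, no limit on activity: Grade 1 by the generic row, Grade 4 by the list.

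**Step 3: the withholding bullet.** Section 10.4.1 lists "Requires inpatient hospitalization or prolongation of existing hospitalization" among the criteria for a serious event; an ER visit alone is not one. Take a related, non-serious event without its own row, seen in the ER and not admitted, with a dose still to come. By the list it is Grade 4 and the Section 7.1 bullet is met. By the generic row it is at most Grade 3 and the bullet is not met. Under the generic row, Grade 4 means hospitalization, which is already serious apart from the listed exceptions. For these events the Grade 4 half of the bullet then adds almost nothing to the serious-event half.

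**Step 4: analysis sets.** Both per-protocol populations require two doses and belong to the double-blind phase. The knock-on exclusion therefore arises only when the second double-blind dose is withheld.

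**Step 5: safety outputs.** Section 9.6 states frequencies by severity for solicited events, which are outside the conflict. It presents unsolicited events by System Organ Class and preferred term, with no severity breakdown stated. The grade of an unsolicited event enters only through its coded value and the optional summaries, listings or narratives for severe events. Of the two records above, dizziness is severe or worse under either definition; the rash becomes so only under the Section 10.4.3 list.

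**The case against.** The strongest reply is that the text has an ordinary reading: use the named rows first, then the Section 10.4.3 list for everything else. On that reading the generic row is a leftover, and nothing shows that sites applied it. This is a fair reading, but the protocol does not state it. The generic row carries a sponsor revision in its Grade 4 cell, which makes it hard to treat as unintended text.

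A second reply is that the withholding effect is narrow. The event must be related. A serious event is caught by the other half of the bullet. A separate bullet already lets the investigator stop vaccination for any related event that in his or her opinion requires it. And a dose must remain. All of this stands and sets the limits of the point.

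A third reply is timing. This is Amendment 7: Section 8.9 ends further boosters except in limited circumstances, Section 8.3.1 confines Safety Subset collection to the double-blind phase, and the Amendment 6 rationale in Appendix 15 already refers to this study's primary analysis. Few vaccination decisions can still change. The grades that are reported can still be made consistent.

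Three stronger readings are tempting, and the protocol does not support them:

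- A reader might infer that any ER visit makes any event Grade 4 under Section 10.4.3. The scope sentence rules this out for every named finding. Nor does Appendix 9 as a whole require hospitalization for Grade 4: nausea reaches it by "Hospitalization; Inability to perform basic self-care functions", fever by a temperature above 40 °C, and diarrhea also by a need for IV fluid replacement.
- A reader might infer that the severity tables mix the two definitions. The only severity frequencies that Section 9.6 states are for solicited events, all of which have their own row.
- A reader might multiply an assumed ER rate by person-time to obtain a number of affected events. The protocol gives no such rate. The product would also include unrelated events, named findings, serious events and events after the last dose.

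**Conclusion.** The contradiction is real and limited. For clinical adverse events without their own Appendix 9 row, two Grade 4 definitions apply, they disagree, and the protocol does not say which governs. The consequences are:

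- the Section 7.1 Grade 4 bullet, for related, non-serious events of this kind seen in the ER without admission while a dose remains, with loss from the two-dose per-protocol sets when that dose is the second double-blind dose;
- the coded grade of such events, and the optional severe-event summaries, listings or narratives.

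In the worked records the difference is one grade for dizziness and three for the rash. The number of affected events is unknown, and no count is claimed. The Stage 1 pausing rules in Section 6.11 do not use AE grades and are unaffected. The conclusion rests only on the wording of Sections 7.1, 9.6, 10.4.1 and 10.4.3, the population definitions and Appendix 9. It takes no position on which grading or withholding rule is right.

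**What to change.** Reconcile Section 10.4.3 with the generic row of Appendix 9 so that a single Grade 4 criterion applies to adverse events without their own row; the sponsor decides which. State that the Grade 4 bullet in both Section 7.1 lists uses that criterion. For reporting, grade the affected events consistently under the single rule, keeping the grade recorded by the site alongside so that investigator assessments are not overwritten. ER attendance is part of the definition of a medically-attended adverse event in Section 8.3.1, so affected records within that collection period should be identifiable.

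The cost is a line in Section 10.4.3 or Appendix 9, a cross-reference in Section 7.1, a grading note to sites, and one derived variable in the adverse event dataset, with some review of individual records. Doses already withheld or given are not altered by this.

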10.4.4. Special Reporting Situations

Safety events of interest on a sponsor study vaccine in an interventional study that may require expedited reporting or safety evaluation include, but are not limited to:

- Known overdose of a sponsor study vaccine
- Suspected abuse/misuse of a sponsor study vaccine
- Accidental or occupational exposure to a sponsor study vaccine
- Medication error, intercepted medication error, or potential medication error involving a Johnson & Johnson medicinal product (with or without patient exposure to the Johnson & Johnson medicinal product, eg, product name confusion, product label confusion, intercepted prescribing or dispensing errors)

Special reporting situations should be recorded in the eCRF. Any special reporting situation that meets the criteria of an SAE should be recorded on the Safety Report Form of the eCRF.

10.4.5. Procedures

All Adverse Events

All AEs, regardless of seriousness, severity, or presumed relationship to study vaccine, must be recorded using medical terminology in the source document and the eCRF. Whenever possible, diagnoses should be given when signs and symptoms are due to a common etiology (eg, cough, runny nose, sneezing, sore throat, and head congestion should be reported as “upper respiratory infection”). Investigators must record in the eCRF their opinion concerning the relationship of the AE to study therapy. All measures required for AE management must be recorded in the source document and reported according to sponsor instructions.

For all studies with an outpatient phase, including open-label studies, the participant must be provided with a “wallet (study) card” and instructed to carry this card with them for the duration of the study indicating the following:

- Study number
- Statement, in the local language(s), that the participant is participating in a clinical study
- Investigator’s name and 24-hour contact telephone number
- Local sponsor’s name and 24-hour contact telephone number (for medical personnel only)
- Site number
- Participant number
- Any other information that is required to do an emergency breaking of the blind

Serious Adverse Events

All SAEs that have not resolved by the end of the study, or that have not resolved upon the participant’s discontinuation from the study, must be followed until any of the following occurs:

- The event resolves
- The event stabilizes
- The event returns to baseline, if a baseline value/status is available
- The event can be attributed to agents other than the study vaccine or to factors unrelated to study conduct
- It becomes unlikely that any additional information can be obtained (participant or health care practitioner refusal to provide additional information, lost to follow-up after demonstration of due diligence with follow-up efforts)

Suspected transmission of an infectious agent by a medicinal product will be reported as an SAE.

Any event requiring hospitalization (or prolongation of hospitalization) that occurs during participation in the study must be reported as an SAE, except hospitalizations for the following:

- Hospitalizations not intended to treat an acute illness or AE (eg, social reasons such as pending placement in long-term care facility)
- Surgery or procedure planned before entry into the study (must be documented in the eCRF). *Note:* Hospitalizations that were planned before the signing of the ICF, and where the underlying condition for which the hospitalization was planned has not worsened, will not be considered SAEs. Any AE that results in a prolongation of the originally planned hospitalization is to be reported as a new SAE.

The cause of death of a participant in a study, whether or not the event is expected or associated with the study vaccine, is considered a SAE.

Information regarding SAEs will be transmitted to the sponsor using a SAE Form and Safety Report Form of the eCRF, which must be completed and reviewed by a physician from the study site, and transmitted in a secure manner to the sponsor within 24 hours. The initial and follow-up reports of an SAE should be transmitted in a secure manner electronically or by facsimile (fax). Telephone reporting should be the exception and the reporter should be asked to complete the appropriate form(s) first.

Adverse Events of Special Interest

AESIs will be carefully monitored during the study by the sponsor. Suspected AESIs must be reported to the sponsor within 24 hours of awareness irrespective of seriousness (ie, serious and non-serious AEs) or causality assessment, following the procedure described above for SAEs and will require enhanced data collection.

10.4.6. Product Quality Complaint Handling

Definition

A PQC is defined as any suspicion of a product defect related to manufacturing, labeling, or packaging, ie, any dissatisfaction relative to the identity, quality, durability, reliability, or performance of a distributed product, including its labeling, drug delivery system, or package integrity. A PQC may have an impact on the safety and efficacy of the product. In addition, it includes any technical complaints, defined as any complaint that indicates a potential quality issue during manufacturing, packaging, release testing, stability monitoring, dose preparation, storage or distribution of the product or the drug delivery system.

Procedures

All initial PQCs must be reported to the sponsor by the study-site personnel within 24 hours after being made aware of the event.

A sample of the suspected product should be maintained under the correct storage conditions until a shipment request is received from the sponsor.

10.4.7. Contacting Sponsor Regarding Safety, Including Product Quality

The names (and corresponding telephone numbers) of the individuals who should be contacted regarding safety issues, PQC, or questions regarding the study are listed in the Contact Information page(s), which will be provided as a separate document.

10.5. Appendix 5: Contraceptive Guidance and Collection of Pregnancy Information

Participants must follow contraceptive measures as outlined in Section [5.1](#). Pregnancy information will be collected and reported as noted in Section [8.3.5](#).

Definition of a Person of Childbearing Potential

A Person of Childbearing Potential

A person is considered fertile following menarche and until becoming postmenopausal unless permanently sterile (see below).

A Person Not of Childbearing Potential

- premenarchal**

A premenarchal state is 1 in which menarche has not yet occurred.

- postmenopausal**

A postmenopausal state is defined as no menses for 12 months without an alternative medical cause.

- permanently sterile (for the purpose of this study)**

Permanent sterilization methods include hysterectomy, bilateral salpingectomy, and bilateral oophorectomy.

Note: If the childbearing potential changes after start of the study (eg, a premenarchal person experiences menarche) or the risk of pregnancy changes (eg, a person who is not heterosexually active becomes active), a person must begin an acceptable effective method of contraception, as described throughout the inclusion criteria.

